## 6.2 Post-Decannulation Surveillance and Anticoagulation Management

Following decannulation, anticoagulation management will be left to the discretion of the treating physician. At 24 to 72 hours post-decannulation, all participants will undergo routine, four-extremity venous ultrasonography for cannula-associated DVT surveillance, in concordance with the current practice for cannula-associated DVT surveillance at Vanderbilt University Medical Center. The exact timing of surveillance and the treatment of any identified DVT will be left to the discretion of the treating physician based on the perceived risks of bleeding relative to benefits of anticoagulation treatment. The presence of any DVT identified by routine surveillance following decannulation will be prospectively recorded.

## 7 Data Collection and Outcome Measures

### 7.1 Data Collection

Data will be collected non-invasively as a part of usual care. No additional data will be obtained beyond that which is obtained by bedside observation and from the electronic medical record. The intervention is defined as the time from randomization until the first of: diagnosis of a major bleeding event, diagnosis of a thrombotic event, placement of an arterial ECMO cannula, decannulation from ECMO, or death.

The following variables will be recorded:

#### **Baseline Variable Collection:**

- Date and time of hospital admission
- Date and time of ICU admission
- Date and time of intubation (if applicable)
- Age
- Assigned gender at birth
- Height
- Weight
- Body mass index
- Self-reported race
- SAPS II score
- Physiologic parameters at randomization (e.g. heart rate, blood pressure, respiratory rate), receipt of vasopressors (agent, dose)
- Measures of mental status and delirium at randomization [e.g. Richmond Agitation-Sedation Score (RASS), Confusion Assessment Method for the ICU (CAM-ICU), Glasgow Coma Scale (GCS)]
- Indication for ECMO
- Respiratory support immediately prior to ECMO cannulation (e.g. nasal cannula, high flow nasal cannula, non-invasive ventilation, or invasive ventilation)
- Fraction of inspired oxygen immediately prior to ECMO cannulation
- Positive end-expiratory pressure immediately prior to ECMO cannulation
- History of chronic lung disease
- History of lung transplantation
- History of thromboembolism
- History of stroke
- History of major bleeding event
- Chronic receipt of anticoagulation
- Receipt of anticoagulation at the time of randomization (e.g. aspirin, clopidogrel, warfarin, direct-acting oral anticoagulants) in the 7 days prior to randomization
- Active medical problems at randomization (e.g. sepsis, septic shock, acute renal failure requiring renal replacement therapy)
- Most recent complete blood count, creatinine, PTT, Anti-Xa, and INR values prior to randomization

- Most recent arterial blood prior to ECMO cannulation
- Date and time of ECMO cannulation
- ECMO configuration at randomization
- Number and location of ECMO cannula sites at randomization
- Manufacturer and model of ECMO circuit at randomization
- Manufacturer and model of oxygenator at randomization
- ECMO settings at randomization (blood flow, revolutions per minute, sweep gas flow, fraction of delivered oxygen)

#### **Assessments between Randomization and Hospital Discharge**

- Date and time of all major bleeding events from randomization to hospital discharge
- Date and time of all thromboembolic events from randomization to hospital discharge
- Anticoagulation strategy at 7 AM each day from randomization to the first of: diagnosis of a major bleeding event, diagnosis of a thrombotic event, placement of an arterial ECMO cannula, decannulation from ECMO, or death; indication for receiving anticoagulation strategy other than intervention strategy
- Randomized assignment to low intensity or moderate intensity anticoagulation strategy
- Number of hours during the intervention period receiving moderate intensity anticoagulation
- Number of hours during the intervention period receiving low intensity anticoagulation
- Date, time, and value of all PTTs and all Anti-XA laboratory results from randomization to 24 hours following decannulation
- Date, time, and type of all major bleeding events from randomization to hospital discharge
- Date, time, and type of all thromboembolic events from randomization hospital discharge
- ECMO blood flow rate, daily during the intervention period
- ECMO fraction of delivered oxygen, daily during the intervention period
- Transmembrane pressures, daily during the intervention period
- Receipt of continuous renal replacement therapy, daily during the intervention period
- Receipt of anticoagulation for continuous renal replacement therapy patency (drug, dose, route of administration), assessed daily during the intervention period
- Volume of packed red blood cells transfused from randomization to 24 hours following decannulation
- Volume of platelets transfused from randomization to 24 hours following decannulation
- Volume of fresh frozen plasma transfused from randomization to 24 hours following decannulation
- Volume of cryoprecipitate transfused from randomization to 24 hours following decannulation
- Lowest documented ECMO blood flow rate during the intervention period
- Date and time of each circuit exchange
- Date and time of each circuit component exchange
- Indication for circuit and circuit component exchanges
- Post-decannulation DVT
- Lowest hemoglobin from randomization to 24 after decannulation
- Lowest documented platelet count from randomization to 24 hours after decannulation
- Highest total and indirect bilirubin values from randomization to 24 hours after decannulation
- Highest LDH value values from randomization to 24 hours after decannulation

- Renal failure requiring renal replacement therapy from randomization to 24 hours after decannulation
- Heparin-induced thrombocytopenia diagnosed by positive serotonin release assay test
- Date and time of decannulation
- Date and time of extubation
- Date of ICU discharge
- Date of hospital discharge
- Date and time of death
- Date and time of arterial cannula placement
- Bleeding event as the primary cause of death
- Thromboembolic event as the primary cause of death

## 7.2 Outcome Measures

### 7.2.1 Primary Efficacy Outcome

- Major bleeding, according to the International Society on Thrombosis and Hemostasis definition, from randomization to 24 hours after decannulation
  - a. Fatal bleeding
  - b. Symptomatic bleeding in a critical area or organ, such as intracranial, intraspinal, intraocular, retroperitoneal, intraarticular or pericardial, or intramuscular with compartment syndrome
  - c. Clinically overt bleeding associated with either a drop in hemoglobin level by at least 2.0 grams/dL or leading to transfusion of two or more units of packed red blood cells

### 7.2.2 Primary Safety Outcome

- Thromboembolic event from randomization to 24 hours after decannulation, defined as:
  - a. Deep venous thrombosis (DVT)
  - b. Acute pulmonary embolism (PE)
  - c. Intra-cardiac thrombosis
  - d. Ischemic stroke
  - e. Acute circuit thrombosis requiring urgent circuit exchange
  - f. Acute arterial thromboembolism

### 7.2.3 Feasibility Outcomes

- Number of patients screened per month
- Number of patients who are eligible per month
- The specific exclusion criteria met (for any patient ineligible for enrollment)
- Reasons for “missed” enrollments (e.g. unavailability of research staff, refusal of clinical team to allow randomization, patient refusal of informed consent)
- Number of patients enrolled per month
- Adherence to the assigned anticoagulation strategy
- Separation between groups in anticoagulation treatment received
- Time from ECMO cannulation to randomization

- Duration of the intervention period, defined as the time from randomization to the first of: diagnosis of a major bleeding event, diagnosis of a thromboembolic event, placement of an arterial ECMO cannula, decannulation from ECMO, or death

#### **7.2.4 Secondary Outcomes**

- Cannula-associated DVT, as measured by four-extremity venous ultrasounds obtained 24-72 hours following decannulation
- Bleeding events per ECMO day
- Thromboembolic events per ECMO day
- Bleeding events from randomization to the first of death or discharge
- Thromboembolic events from randomization to the first of death or discharge
- Circuit or circuit component exchange required during ECMO support
- ECMO circuit durability, calculated as the number of calendar days from randomization to death or decannulation divided by the number of ECMO circuits used
- RBC transfusion volume per ECMO day, calculated as the total volume of packed red blood cells transfused from randomization to death or decannulation divided by the number of calendar days during this period
- New diagnosis of HIT from randomization to the death or decannulation from ECMO, as measured by clinically obtained serotonin release assay
- Lowest documented platelet count from randomization to 24 hours after decannulation
- Highest Total and indirect bilirubin values from randomization to 24 hours after decannulation
- Highest LDH value values from randomization to 24 hours after decannulation
- Death attributable to a major bleeding event
- Death attributable to a thromboembolic event
- Ventilator-free days
- ECMO-free days
- ICU-free days
- Hospital-free days
- In-hospital mortality

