### 2.1 Study Aims

- **Primary aim:** To demonstrate feasibility of a future large, multi-center randomized controlled trial comparing low intensity to moderate intensity anticoagulation among adults receiving V-V ECMO by demonstrating the ability to recruit and randomize participants, adhere to assigned anticoagulation strategy, and demonstrate adequate separation between groups in therapy delivered and intensity of anticoagulation achieved with the assigned anticoagulation strategies.
- **Secondary aim:** To define and measure the primary efficacy, primary safety, and secondary outcomes of a future large, multi-center randomized controlled trial comparing low intensity vs moderate intensity anticoagulation among adults receiving V-V ECMO.

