2) Circuit thrombosis – fibrin and thrombus can accumulate throughout the components of the ECMO circuit (generally the oxygenator) over time due to the non-biologic surfaces of the device and turbulent areas of blood flow. The burden of thrombus may either gradually or acutely worsen requiring a controlled or emergent circuit component exchange. When a circuit component acutely fails to operate, and during any circuit component exchange, the patient may be inadequately supported by ECMO temporarily and may experience clinical compromise, including hypoxemia, acidemia, hypotension, symptomatic bradycardia, and other cardiac arrhythmias. During the majority of circuit exchanges the physiologic derangements are transient and without deleterious consequences; nevertheless, in the most severe circumstances, these may lead to cardiac arrest. All patients receiving ECMO are at risk for requiring a circuit or circuit component exchange, and circuit or circuit component exchange are frequently required for patients receiving V-V ECMO regardless of anticoagulation strategy. Compared to moderate intensity anticoagulation, a strategy of low intensity anticoagulation could increase the risk of circuit thrombosis, but based on available data, this is unknown.

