## 12 Statistical Considerations

### 12.1 General Considerations

We will present summary tabulations by treatment group. For categorical variables, the number and percentage of patients within each category (with a category for missing data as needed) of the parameter will be presented. For continuous variables, the number of patients, median and interquartile range as appropriate, will be presented.

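### The ECMO circuit durability formula treats the last, still-working circuit as finished, so when exchanges are infrequent it reflects run length more than circuit life.

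*Combined protocol and SAP*

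**What the plan says.** The Trial Summary and section 7.2.4 both list, as a secondary outcome, "ECMO circuit durability, calculated as the number of calendar days from randomization to death or decannulation divided by the number of ECMO circuits used". Neither says how to treat the circuit in use when the run ends. Section 12.1 states "For continuous variables, the number of patients, median and interquartile range as appropriate, will be presented", and section 12.3 confines the analysis to descriptive statistics; no time-to-event method appears.

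Two other outcomes touch on circuit failure. Section 7.2.4 lists "Circuit or circuit component exchange required during ECMO support", and the primary safety outcome in section 7.2.2 includes "Acute circuit thrombosis requiring urgent circuit exchange". On frequency, section 9.1.1 says only that "circuit or circuit component exchange are frequently required for patients receiving V-V ECMO regardless of anticoagulation strategy".

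The secondary aim in section 2.1 is "To define and measure the primary efficacy, primary safety, and secondary outcomes of a future large, multi-center randomized controlled trial". Section 7.1 already collects the date and time of every circuit exchange and every component exchange (recorded separately), their indications, and the dates and times of decannulation and death.

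**The concern.** A lifetime that ends because the patient was weaned or died is censored: the circuit lasted at least that long. The formula records it as an observed failure. Early weaning or early death therefore lowers the score although the circuit worked, and a long run raises it.

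This matters because section 9.1.1 names circuit thrombosis as a possible risk of low intensity anticoagulation, and durability is the listed outcome that purports to measure circuit life. If the arms differ in run length, through recovery or death, that difference can appear as a difference between circuits. Because the pilot is meant to define outcomes for the larger trial, the definition may be carried forward.

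The companion outcomes do not repair this. Any exchange during support is not adjusted for time at risk. The thromboembolic rate counts only acute thrombosis that needs urgent exchange, whereas section 9.1.1 says thrombus may also build up gradually and lead to a controlled exchange.

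**Working it through.** **Inputs from the plan.** The formula (section 7.2.4), at most 30 patients (12.4) and 1:1 allocation (5.5), hence about 15 per arm. The plan gives no circuit life, exchange rate or run length, so it has no figure to reproduce.

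**Assumptions.** Constant exchange hazard with mean circuit life *m* of 5 to 30 days; run length *T* gamma distributed with shape 2 and mean *r* of 7 or 14 days.

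**Step 1: expected score.** With *X* exchanges, the score is *T*/(1+*X*). Given *T*, *X* is Poisson with mean *T*/*m*, so the expected score is *m*(1 − exp(−*T*/*m*)). Averaging over the gamma runs gives *m*[1 − (1 + *r*/(2*m*))^−2]. For *m* = 30 and *r* = 7: (1 + 7/60)^−2 = 0.802, and 30 × 0.198 = 5.9. The closed form was confirmed with 1,000,000 simulated runs.

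| Mean circuit life, same in both arms | Mean score, 7-day runs | Mean score, 14-day runs |
|---|---|---|
| 30 days | 5.9 | 10.3 |
| 15 days | 5.1 | 8.0 |
| 10 days | 4.5 | 6.5 |
| 5 days | 3.3 | 4.1 |

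The circuits in each row are identical; only the runs differ. With identical 20-day circuits and 15 patients per arm, the arm with 14-day runs has the higher mean score in about 97% of simulated trials. A separate simulation with lognormal runs and 20-day circuits agrees: the median score goes from 5.4 to 8.6 days as the median run goes from 7 to 14, while total days divided by total exchanges stays at about 20.

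**Step 2: when run length dominates.** The proportional sensitivity of the expected score to mean run length is 2/[(1+*u*)(2+*u*)], with *u* = *r*/(2*m*). Setting it to 0.5 gives *u*² + 3*u* − 2 = 0, so *u* = 0.56 and *r*/*m* = 1.12 expected exchanges per run. For fixed runs the threshold is 1.26. Below about 1.1 to 1.3 exchanges per run, run length moves the score more than circuit life does.

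**Step 3: equal runs, true twofold difference in circuit life.** 200,000 simulated trials, 15 per arm; share in which the better arm ranks worse:

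| Circuit life, mean run | Mean score | Median score | Exchange rate |
|---|---|---|---|
| 30 vs 15 days, 7-day runs | 28.7% | 32.6% | 14.1% |
| 30 vs 15 days, 14-day runs | 16.6% | 21.3% | 6.4% |
| 20 vs 10 days, 14-day runs | 9.8% | 14.0% | 3.1% |
| 10 vs 5 days, 7-day runs | 9.9% | 14.1% | 3.1% |
| 10 vs 5 days, 14-day runs | 2.6% | 4.5% | 0.4% |

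Repeat simulations moved these figures by a few tenths of a percentage point.

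**Step 4: unequal runs.** Take 8-day runs in the better arm and 14-day runs in the worse arm. Expected scores, better versus worse, are 6.6 vs 8.0 for 30 vs 15 days (order reversed), 6.1 vs 6.5 for 20 vs 10 days (reversed) and 4.9 vs 4.1 for 10 vs 5 days (correct). Holding the worse arm at 14-day runs, reversal needs the better arm's runs to be shorter by more than 28%, 37% and 56% respectively.

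**The case against.** The strongest reply is about weight. Durability is one of 19 secondary outcomes in a descriptive pilot of at most 30 patients with no inferential tests, and the raw times are collected, so a better summary can be produced later. ECMO-free days, mortality and duration of the intervention period are also reported, and would show an imbalance in run length. All of this is true and limits the importance of the point. But seeing the imbalance does not correct the score, and an aim of the pilot is to settle the outcome definitions.

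The neighbouring outcome of any exchange also does better than durability in some settings. For 30 vs 15 days with 7-day runs, the proportion with an exchange misranks the arms in 18.6% of trials, between mean durability and the rate. Where durability reverses in step 4, the proportion points the right way: using 1 − (1 + *r*/(2*m*))^−2, it is 22% vs 54% and 31% vs 65%. That is partly because the better arm's runs are shorter. In the opposite pattern, 30-day circuits with 14-day runs against 15-day circuits with 7-day runs, *r*/(2*m*) is 0.233 in both arms. The expected proportion is then 34% in each, and a twofold difference in circuit life disappears.

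Two further cautions stand. The phrase in section 9.1.1 leans towards frequent exchanges, where the distortion is smaller; but it gives no rate and pools component with whole-circuit exchanges, while durability counts circuits. And the exchange-rate figures assume the same hazard in every patient. With gamma variation between patients (coefficient of variation 1, also an assumption), the rate misranks in 9 to 19% of equal-run trials. The mean score then misranks in 20 to 34%, so the advantage remains.

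**Conclusion.** The concern holds. That the last circuit is censored follows from the formula alone and needs no outside figure. How much it matters depends on exchange frequency, which the documents do not give: run length dominates below roughly 1.1 to 1.3 exchanges per run, and above that the distortion shrinks but does not vanish. Under the stated assumptions the score misranks the arms at least twice as often as an exchange rate even when runs are equal. A reversal of the expected order, by contrast, needs a marked difference in run length. This is a worthwhile improvement to a secondary outcome and does not threaten the pilot's feasibility aim. Confidence in the size is moderate, because every circuit life and run length used here is assumed.

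**What to change.** - Report circuit exchanges per 100 ECMO-days by arm (total exchanges over total elapsed ECMO-days from randomization), in place of durability or beside it. This matches the per-ECMO-day form already used for bleeding and thromboembolism.
- Add the cumulative incidence of first exchange from randomization, with decannulation and death as competing events.
- State whether a component-only exchange counts. The plain wording of durability suggests it does not, but the plan should say so.
- As a separate, minor reconciliation: for red-cell use per ECMO day, section 7.2.4 gives this formula: "total volume of packed red blood cells transfused from randomization to death or decannulation divided by the number of calendar days during this period". However, the only red-cell field listed in section 7.1 is "Volume of packed red blood cells transfused from randomization to 24 hours following decannulation". Record the volume up to death or decannulation as its own field.

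The cost is outcome wording and one transfusion field; the exchange, decannulation and death times are already collected. The rates will be imprecise: with 15 patients per arm and 7-day runs, 15 × 7/30 = 3.5 exchanges per arm for 30-day circuits and 15 × 7/15 = 7 for 15-day circuits.

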**Secondary outcomes:**

- Cannula-associated DVT, as measured by four-extremity venous ultrasounds obtained 24-72 hours following decannulation
- Bleeding events per ECMO day
- Thromboembolic events per ECMO day
- Bleeding events from randomization to the first of death or discharge
- Thromboembolic events from randomization to the first of death or discharge
- Circuit or circuit component exchange required during ECMO support
- ECMO circuit durability, calculated as the number of calendar days from randomization to death or decannulation divided by the number of ECMO circuits used
- RBC transfusion volume per ECMO day, calculated as the total volume of packed red blood cells transfused from randomization to death or decannulation divided by the number of calendar days during this period
- New diagnosis of HIT from randomization to the death or decannulation from ECMO, as measured by clinically obtained serotonin release assay
- Lowest documented platelet count from randomization to 24 hours after decannulation
- Highest Total and indirect bilirubin values from randomization to 24 hours after decannulation
- Highest LDH value values from randomization to 24 hours after decannulation
- Death attributable to a major bleeding event
- Death attributable to a thromboembolic event
- Ventilator-free days
- ECMO-free days
- ICU-free days
- Hospital-free days
- In-hospital mortality

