### **12.4 Sample Size**

Given their small size, pilot trials have limited ability to estimate effect sizes that will be observed in subsequent large trials trial. As this is a descriptive pilot, feasibility trial, no formal sample size calculation has been undertaken. We will plan to enroll to the first of 30 total patients across all sites or up to November 12, 2023

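### RBC volume per ECMO day is defined up to death or decannulation, but the only RBC volume item listed for collection runs to 24 hours after decannulation, so the listed variables do not yield the defined numerator

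*Combined protocol and SAP*

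**What the plan says.** The outcome appears in the Trial Summary and again in Section 7.2.4. Its numerator is "RBC transfusion volume per ECMO day, calculated as the total volume of packed red blood cells transfused from randomization to death or decannulation". The total is then "divided by the number of calendar days during this period", so numerator and denominator share one end point.

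The list in Section 7.1 of assessments between randomization and discharge contains a single red cell volume item: "Volume of packed red blood cells transfused from randomization to 24 hours following decannulation". Platelets, plasma and cryoprecipitate have the same window.

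Other items in that list carry more detail. Coagulation results are time-stamped: "Date, time, and value of all PTTs and all Anti-XA laboratory results from randomization to 24 hours following decannulation". Circuit flow is serial: "ECMO blood flow rate, daily during the intervention period". The end of the run is recorded as "Date and time of decannulation". On sources, Section 7.1 says: "No additional data will be obtained beyond that which is obtained by bedside observation and from the electronic medical record".

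Section 12 plans description only, without hypothesis tests. Section 12.4 states that "no formal sample size calculation has been undertaken" and caps enrollment at 30 patients, or fewer if the calendar limit comes first.

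**The concern.** The outcome and the data item meant to supply it stop at different times, and nothing in the protocol says how the extra 24 hours are to be removed. An analyst working from the listed variables would have to use a total that covers a longer period than the denominator, or go back to the chart.

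Using the total would do more than shift every value by a constant. The excess would be largest in short runs and absent in patients who die on ECMO, so the measure would partly reflect run length and survival. It would also include blood given when, under Section 6.2, anticoagulation is already at the treating physician's discretion.

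This deserves attention even in a pilot. The secondary aim in Section 2.1 is to define and measure the outcomes of the future trial, and the Background cites lower transfusion requirements as an observed advantage of low intensity anticoagulation.

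**Working it through.** The plan gives no figure for this outcome, so there is none to reproduce. The check compares the two windows and then sizes the consequence.

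**Windows**

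| Element | Starts | Ends | Source |
|---|---|---|---|
| Outcome numerator | randomization | death or decannulation | Section 7.2.4 |
| Outcome denominator (calendar days) | randomization | death or decannulation | Section 7.2.4 |
| RBC volume item | randomization | 24 hours after decannulation | Section 7.1 |

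**Formula.** Let V_on be the volume given up to death or decannulation, V_post the volume in the 24 hours after decannulation, and D the calendar days from randomization to death or decannulation.

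- Outcome as defined: V_on / D.
- Outcome from the listed total: (V_on + V_post) / D.
- Excess: V_post / D. A patient who dies on ECMO has no post-decannulation window, so V_post = 0 and the excess is 0.

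**Absolute size.** V_post is not in the documents. Assume 600 mL (two units of 300 mL):

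- D = 5: 600 / 5 = 120 mL/day.
- D = 20: 600 / 20 = 30 mL/day.
- V_post = 0: no excess at any D.

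**Relative size.** The excess as a percentage of the true rate r is 100 × V_post / (r × D). Both r and V_post are assumptions.

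| D (days) | r = 100 mL/day, V_post = 300 mL | r = 200 mL/day, V_post = 300 mL |
|---|---|---|
| 2 | +150% | +75% |
| 5 | +60% | +30% |
| 10 | +30% | +15% |
| 20 | +15% | +7.5% |
| 30 | +10% | +5% |

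With V_post = 600 mL each percentage doubles.

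**Between arms.** Suppose the true rates are equal, V_post is 300 mL per patient and only run length differs.

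- Runs of 5 versus 10 days: 300/5 − 300/10 = 60 − 30 = 30 mL/day of spurious difference.
- Runs of 10 versus 12 days: 300/10 − 300/12 = 30 − 25 = 5 mL/day.
- Equal run lengths: none.

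**After the fix.** With the volume cut at death or decannulation, the excess is 0. At r = 100 mL/day and V_post = 300 mL, a 5-day run falls from (500 + 300)/5 = 160 to 500/5 = 100 mL/day.

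**The case against.** **The definition already excludes the extra blood.** Section 7.2.4 stops at decannulation, and no section says that the 24-hour total will be the numerator. This stands. A reader might infer that post-decannulation blood does enter the outcome. The documents show only that the listed item does not match, so the inflation is conditional on that item being used as collected.

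**The volume is recoverable.** Data come from the medical record, the decannulation time is collected, and the case report form is not among the documents. This also stands. It would be too strong to say that the numerator is lost; it is missing from the listed variables only. But going back to the chart is a step the plan does not mention, and Sections 13 and 14 remove the identifying links at publication.

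**The longer window has a plausible purpose.** The primary efficacy outcome runs to 24 hours after decannulation and counts overt bleeding that leads to transfusion of at least two red cell units. The protocol does not give this as the reason, but the windows agree. The item should therefore be split, not shortened.

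**The calendar-day denominator.** A reader might want to replace it with elapsed hours. The documents do not make it an error: it is a stated convention, shared with circuit durability. Elapsed time would also make very short runs more extreme. For an assumed 6-hour run with 600 mL it gives 600/0.25 = 2,400 mL/day, against 600 if counted as one day. The protocol does not say whether both end dates count. If they do, part of the post-decannulation window nominally falls within the denominator (12 of 24 hours for a noon decannulation).

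**Little depends on it.** This is one of 19 secondary outcomes. Section 12.1 summarizes continuous variables by median and interquartile range, which resist a few extreme values, although Section 12.3 also lists the mean. This limits the weight of the point but does not reconcile the two windows.

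**Conclusion.** The point holds as a conflict between two stated windows: the outcome ends at death or decannulation, and the only listed red cell volume ends 24 hours after decannulation with no means of separating the parts. The defined numerator cannot be derived from the listed variables without returning to the medical record.

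The size of the error if the listed total is used is V_post / D per decannulated patient. The figures of 120 and 30 mL/day rest on an assumed 600 mL, and the excess disappears if no blood is given after decannulation. The statement that short runs are affected most assumes that V_post does not depend on run length.

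Two further inferences are not supported. The documents do not say that blood in this window would be for bleeding at the cannula sites. They also do not guarantee 15 patients per arm, because 30 in total is a maximum.

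The practical impact is modest: a descriptive secondary outcome, no testing, and no effect on the feasibility outcomes or the definition of the primary bleeding outcome. The correction is worth making because it is cheap and because defining outcomes for the later trial is one of the pilot's aims.

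**What to change.** In Section 7.1, replace the single red cell volume item with two:

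1. volume from randomization to the first of death or decannulation;
2. volume in the 24 hours after decannulation.

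Compute RBC volume per ECMO day from item 1 only, and keep the calendar-day denominator. Items 1 and 2 together still cover the window of the primary bleeding outcome.

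The cost is one additional field from the same medical record and slightly more data entry. For patients already entered, item 1 has to be re-extracted while the link to the record still exists. Clinical management does not change.
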